11.5 Please provide a justification for your sample size

Since this is a discovery-based study of a novel topic, limited data are available with which to perform a power analysis. Thus we used a G*Power for a general comparison analysis without needing to root firmly in one specific variable.

If we are able to enroll 150 participants (a minimum of 92 post-attrition), assuming an effect size of .2, we will achieve 90% power. Effect size assumptions were taken from Tomazoni et al. 2016 based on the comparison of control versus PBMT with regards to biomarkers of gene expression that we assume to be an acceptable proxy for our primary comparison with regards to our biomarkers of concern. Significance threshold for power calculations was considered to be .01 to account for false discovery rate within our set of primary biomarker outcomes. Power calculations were performed using the WebPower package and the R Programming language.

11.6 Data Analysis Plan: Complete description: Background, Objectives, Design, Step by Step how the project is going to be done, Data analysis plan:

Aim 1 will be evaluated by comparing the PRP only and the PRP + PBMT treatment arms at six weeks relative to baseline. Generalized additive models predicting the fractional change in outcome measure at 6 weeks will be used.

Aim 2 will compare across all four treatment arms and will use Multi-Level models comparing the three treatment arms across time points and including random effects.

Aim 1 will include biomarker measures only; Secondary Aim 2 will include both biomarker measures and self-reports.

Hypothesis tests will be two-tailed and statistical significance will be considered at the putative threshold ($\alpha=0.05$). Any secondary P-values will be subject to a false discovery rate adjustment in keeping with best statistical practices. Multilevel models will incorporate random effects to account for repeated measures, using distribution families and link functions appropriate for the outcomes of interest, determined using QQ plots analyzed for best model fit. All statistical analyses will be performed using the R Programming language.

Clinical outcomes (pain scores) will be evaluated via ANOVA and post-hoc tests (Tukey's HSD test). A non-parametric alternative will be used if assumptions are not met.

Molecular Analyses:

DNA/RNA Analyses

DNA/RNA analyses will be performed using the software Galaxy or Geneious or any similar software packages such as Bioconductor for the R programming language. Specific statistical methods will depend on the variables of interest, but will include Fisher's exact test or Chi-square test for categorical data, logistic or linear regression for dependent variables with binary and continuous outcomes, respectively, and PCA, t-SNE, or U-MAP for dimensionality reduction, the first step in unsupervised clustering. The unsupervised clustering techniques that follow will include those listed above for microbiome profiling but may also include techniques better suited to specifically Cartesian coordinate data such as k-means. The latter would be accomplished following projection of the data into a Cartesian plane, e.g. via non-metric multidimensional scaling (NMDS). Data collected via the nCounter platform, qPCR data, or any data collected using a similar technology will be analyzed in accordance with the manufacturer's recommendations (e.g., t-test, linear regression, etc.). Sequence alignment for the purpose of biomarker identification (e.g., SNP detection) will be performed using Bowtie2 or similar software as standalone command line based software or via a graphic user interface (GUI) embedded within Galaxy, Geneious, or another package. Differential expression analysis for transcriptomic data will be performed using standard tools and workflows (e.g., Salmon, Kallisto, Sleuth, DESEQ2, edgeR, Coordinate Covariation Analysis, epigenomix, etc.).

Proteomic Analyses

Maximum-likelihood techniques based on the negative binomial distribution will be used to model proteomics count data and Wald statistics, two-tailed t-test, analysis will be utilized to analyze the primary and secondary outcomes. Any missing data that cannot be obtained via chart review or interview of the caring provider will be omitted and documented as such. In some case where the confounding variables cannot be eliminated or minimized through experimental design, the confounding variables will be included in the analysis to control for their effects. Data analysis will be conducted using both standalone proteome discoverer with Sequest, Mascot search engine and R-programming languages established for high throughput proteomics data analysis here in DCI. For orthogonal validation data sets will be analyzed with the various statistical algorithms that are established in DCI.

Correlation Analyses

Associations between clinical, demographic, and gene expression, genetic, and microbial data will be identified by calculating correlations and other metrics of associations. For example, Pearson's correlation will be used to detect presumptive linear associations. Spearman's correlation or Kendal's tau will be used to detect non-linear but still monotonic relationships. Hoeffding's D statistic will be used to detect more complex, possibly non-monotonic, relationships. Multivariate approaches (e.g., linear or logistic regressions) will be used to control for potential covariates.

Predictive Analytics

We will model return to duty time rate and time using a combination of analytic methods that enable prediction and inference. First, we will use methods such as logistic regression and decision trees to support inference about the factors that contribute the most to returning to duty. Second, we will use methods such as multivariate regression, support vector machines, and neural networks to predict the rate of and time to return to duty. The latter approach will enable the integration of a broader array of variables than the former methods. The overall result will be inclusion of not only pre-operative and post-operative outcome variables but also biomolecular signatures.

12.0

Participant Information

12.1 Subject Population:

DEERS eligible adults (age 18-64, inclusive) diagnosed with knee OA

12.2 Age Range:

Check all the boxes that apply. If the age range of potential subjects (specimens, records) does not match the range(s) selected, please specify in the text box.

- 0-17
- 18-24
- 25-34

- 35-44
- 45-54
- 55-64
- 65-74
- 75+

12.3 Gender:

- Male
- Female
- Other

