Prior to receiving their assigned study treatment, participants will complete a Demographics CRF (Appendix C) and a Baseline Data Collection CRF (Appendix D). These questionnaires collect relevant data including: personal demography, military and employment demography, injury demography, and medical history, Fitzpatrick Skin Phototype, and validated self-reports.

A blood draw and a knee joint aspiration for synovial fluid will be conducted at baseline to assess for orthobiologics related to knee OA management (A complete list can be found in Section 10.2). Blood and synovial fluid date collection will be documented on the Baseline Data Collection CRF (Appendix D).

Blood Collection:

All team members will be trained, specifically in the methods of blood collection, safety, laboratory requirements, and processing, appropriate for their role in this study. These individuals will complete all training required by the MAMC lab, which can include hazardous materials handling, and biohazard safety.

The specimen collected in this study will not be used for clinical purposes.

An adequate amount of peripheral blood (approximately 11 ml) will be drawn by an experienced phlebotomist on the research team following standard sterile techniques. Blood will be collected into the appropriate blood collection tubes:

1. K2/EDTA Blood Tube 1 at 4ml
2. Heparin Blood Tube 1 at 4ml
3. DNA/RNA Shield Blood Collection Tube 1 at 3ml

The blood sample will be labeled with a sample ID (different from the study ID) and study visit, and transported to MAMC Department of Clinic Investigation (DCI) for storage and processing. Any excess blood sample will be safely discarded per standard protocol. Ice will be utilized for transportation, when necessary.

The blood samples will be processed by the DCI staff as described in the "Sample Processing" section below.

Synovial Fluid Collection:

Synovial fluid will be collected by the study team, including Orthopedic Surgeons, Physician Assistants, and Physicians at 3 possible locations:

1. MAMC Orthopedic Clinic
2. MAMC Sports Medicine Clinic
3. MAMC Physical Medicine and Rehabilitation

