Synovial fluid will be aspirated according to standard of care (SOC) guidelines. If, at the time of joint aspiration, there is a "dry tap" (i.e., no fluid is returned), the provider will lavage the joint with a standardized quantity (10ml) of sterile Normal Saline and then aspirate the lavage. There are no harmful effects from lavaging the synovial joint with sterile saline.

The synovial fluid will be labeled with a sample ID and study visit, and transported to MAMC Department of Clinic Investigation (DCI) for storage and processing. Any excess synovial fluid will be safely discarded per standard protocol. Ice will be utilized when necessary.

Synovial fluid processing and storage are outlined below in respective sections.

The research team will maintain a biospecimen sample master key that links the sample IDs to the participant study IDs. No PII/PHI will be stored with the biospecimen sample key.

Randomization:

Participants that meet final eligibility criteria will be randomized to a study arm using a computer-generated randomization model prepared by the study biostatistician, to assign participant 1:1:1:1 across all study arms (PT, PT+PRP, PT+PBMT, or PT+PRP+PBMT).

Study Intervention:

Study interventions will be documented in the participant's EMR and on the Study Treatment Documentation Log (Appendix F).

Standard of Care (SOC) Physical Therapy (PT):

All participants will complete a standard PT program addressing individual strength, mobility, and flexibility deficits in both proximal and distal muscle groups. The provider may also use other modalities to address distal issues. If a participant has not been placed on profile at the time of consent, a profile may be written by the study medical provider to ensure limitation of activities, as appropriate.

The PT treatment participants receive in this study will be standard of care; that is, the PT treatment regimen will not be standardized across study participants and/or dictated by study-specific criteria. PT treatments will be recorded on a Chart Review CRF (Appendix I).

SOC PT + Platelet-Rich Plasma (PRP):

In addition to SOC PT, participants assigned to PT+PRP group will receive PRP treatment, as outlined below.

PRP Preparation:

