Samples stored at MAMC DCI will be coded using the Biospecimen Master Key (Appendix S) that links the sample IDs to the participant study IDs. The Biospecimen Master Key will be kept on a CAC-enabled, secure laptop.

MAMC DCI will maintain samples collected during the course of this protocol until they are exhausted. Tracking and storage of biological samples will be performed according to established SOPs with protocol specific modifications. MAMC DCI will maintain de-identified sample IDs and information regarding: samples processed/received, sample storage location/access/usage, quality control information (acquisition of correct sample; rapid sample preservation; timely transportation to the repository; routine and continuous monitoring). Study team members will visually inspect the samples for integrity and verify the date/time the samples were collected.

All specimens will be coded and specimen information will be stored electronically. The PI of this study will be the point of contact for the access and utilization of biological samples for experimental procedures.

Specimen Processing

These sample analyses will provide insight into the internal biological cascade/changes of protein expression over time, that may inform the effectiveness of treatment/management of knee OA with PRP and PRP + PBMT treatments.

We plan to quantify protein expression, and we may do so using protein panels (e.g., a Bio-Plex kit) or lower throughput methods (e.g., ELISA or Western blot), if necessary. We may also attempt to use flow cytometry. Substrate for protein expression analyses will be plasma, synovial fluid, or synovial fluid pellets.

Note: It is possible that there could be an insufficient number of cells in the synovial fluid pellet to perform flow cytometry. In the future, if time and resources allow, we may also perform mass spectrometry, as our sample collection methods are compatible with mass spectrometry. At the moment, however, we have no immediate plans to use the technique. If we choose to pursue this technique in the future, we will consult with mass spectrometry experts.

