- RNA - Data will be generated in fastq format (if performing sequencing, e.g., with a MiSeq, NextSeq, MinION) and summarized as counts at the isoform or gene level. To arrive at the count level, raw data will be processed by performing alignment, pseudo-alignment, or any other mapping technique. Different software may be used to do this, e.g. Sleuth. Statistical analyses will be performed using standard workflows, e.g. DESeq2, edgeR. We may also use RNA quantification methods such as the nCounter, PCR arrays, and qPCR. For the latter methods, we will use the manufacturer's software (e.g. nSolver), the delta delta Ct method, or standard curves for absolute quantification. We will use loading controls such as GAPDH, RPLP0, or similar when needed.
- Protein - We will perform ELISAs (generate spectrophotometric data), Western blots (generate densitometric data), use arrays or multi-plex or other intermediate throughput techniques (e.g., Olink, BioPlex), mass spectrometry data (outputs vary but will be summarized into counts or relative expression levels), or other relevant methodologies.

Sample processing is as follows:

- *Synovial Fluid:*
 - Synovial fluid (SF) will be collected in a 1.5 mL Eppendorf tube (ept).
 - SF sample will be transferred to the lab on ice.
 - SF sample will be centrifuged at 1500g for 15 min in a refrigerated centrifuge to clear SF from cellular debris.
 - Supernatant (synovial fluid) will be immediately transferred into a clean 1.5 mL ept.
 - Protease inhibitor will be added at 1X final concentration (100-fold dilution of the original 100X).
 - 200-500µL of SF will be aliquoted into a pre-labeled 1.5 mL tube and stored at -80° C.
- *Proteomics analysis:*
 - 4-5 mL of blood will be collected into a sodium heparin tube, and an additional 4-5 mL of blood will be collected into a K2 EDTA tube.
 - Blood samples will be transferred to the lab within 20 minutes of collection.
 - Blood samples will be centrifuged at 2000 g for 15 minutes using a refrigerated centrifuge.
 - The top liquid component (plasma) will be immediately transferred into a clean 15 mL polypropylene conical tube.
 - Protease inhibitor will be added at 1X final concentration (100-fold dilution of the original 100X).
 - 200-500 µL of plasma will be aliquoted into a pre-labeled 1.5 mL tube and stored at -80°C.
- *DNA/RNA analysis:*
 - 3ml of blood will be drawn into a DNA/RNA Shield Blood Collection Tube.
 - Blood samples will immediately be inverted 10 times (gently).

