For categorical variables, statistical methods may include tests such as the Fisher's exact test, Chi-square test, McNemar's test, or binomial test. For ordinal variables that do not approximate a continuous variable, tests such as ordinal logistic regression will be performed. For ranked data, tests such as Friedman's test will be used. For continuous random variables (ratio or interval types) or ordinal data that approximates a continuous random variable (e.g., Likert scale), t-tests will be used. The Wilcoxon signed rank test or Wilcoxon rank sum test will be used if the assumptions for the t-test do not hold. The normality assumption may be evaluated with a test that is appropriate given the sample size, objective, and intended audience, e.g., Shapiro-Wilk test, Jarque-Bera test, Kolmogorov-Smirnov test, or Anderson-Darling test. For analyses with more than two groups in the single independent variable or for analyses with more than one independent variable, single or multi-way ANOVAs will be performed, respectively. If a continuous variable is a potential covariate, then an ANCOVA will be performed. Post hoc tests will include tests such as Tukey's, Dunn's, Dunnett's, or pairwise univariate tests with false discovery rate correction, depending on the objectives of the analysis. Sequencing data will be analyzed using techniques that include negative binomial regression, PERMANOVA, and ANOSIM. Clustering will be performed using techniques such as hierarchical, k-means, k-medoids, Gaussian mixture models. These methods will attempt to minimize (or maximize depending on the metric) an error metric such as silhouette score, Akaike Information Criterion, or Bayesian Information Criterion with the specific metric being selected based on the best practice in the field, e.g., silhouette score for k-means. Clustering may be performed with or without first performing dimensionality reduction using Principal Components Analysis, Non-metric Multi-Dimensional Scaling, t-SNE, U-MAP, or another similar technique, depending on the data types, number of variables, and objectives. When analytic methods are unavailable, bootstrapping may be performed to estimate uncertainties, e.g. confidence intervals. Alternatively, if Bayesian methods are applied, then credible intervals will be calculated. When decision trees and decision-tree based methods (e.g., random forest, decision jungles) are used, feature importance may be calculated. When developing predictive models, both simple, explainable models (e.g., linear and logistic regressions) will be used when possible. When incorporating larger numbers of variables, neural network based models may be used. When such methods are applied, the optimum number of layers, dropout, activation functions, nodes, and other elements of model architecture will be determined empirically. Data will be split into training, cross validation, and testing groups in accordance with best practices in the machine learning and artificial intelligence fields. Regarding correlation analyses, correlations will be identified via methods that include Pearson's, Spearman's, and Kendall's tau. The specific method will be selected based on the bivariate distribution of the data, e.g. monotonic and linear vs. monotonic but not linear. Hoefding's D statistic may be calculated for non-monotonic relationships.

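### Aim 1 models fractional change with no baseline term, family, link or log scale, and no rule names synovial samples diluted by dry-tap lavage; both gaps can cost power and are cheap to close

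*Combined protocol and SAP*

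**What the plan says.** **Model.** Section 11.6 limits Aim 1 to the two PRP-containing arms and to biomarkers, and gives one sentence on method: "Generalized additive models predicting the fractional change in outcome measure at 6 weeks will be used". The sentence in 11.6 on choosing family and link has the multilevel models as its subject, and those serve Aim 2. Section 11.1 allows ANCOVA when a continuous variable may be a covariate, without naming Aim 1 or the baseline biomarker. It also gives a fallback for t-tests: "The Wilcoxon signed rank test or Wilcoxon rank sum test will be used if the assumptions for the t-test do not hold".

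**Data.** Section 10.1 provides the baseline value: "A blood draw and a knee joint aspiration for synovial fluid will be conducted at baseline". Both samples are taken again at 6 weeks. On assays, "Substrate for protein expression analyses will be plasma, synovial fluid, or synovial fluid pellets". Some assay methods already work on a log or count scale: for qPCR, the laboratory software, "the delta delta Ct method, or standard curves for absolute quantification"; for sequencing and proteomic counts, negative binomial models.

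**Lavage.** After a dry tap, "the provider will lavage the joint with a standardized quantity (10ml) of sterile Normal Saline and then aspirate the lavage". Section 10.1 labels the sample with an ID and visit. The synovial steps include "SF sample will be centrifuged at 1500g for 15 min in a refrigerated centrifuge to clear SF from cellular debris", then protease inhibitor, aliquoting and freezing. Dilution by lavage is not mentioned. Section 11.1, and 11.6 under Proteomic Analyses, say in general terms that confounders will be put into the models.

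**Outliers.** The opening of Section 11.1 removes outliers judged erroneous. Its later Outliers paragraph lets outliers be excluded, or replaced by a random value, the median or an imputed value, without requiring an error. A with/without comparison is planned, but the primary result is not named.

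**The concern.** A ratio to baseline carries the noise of the baseline measurement, and for a right-skewed marker it has a long upper tail. A comparison of mean fractional changes is then driven by a few participants with low baseline values. The baseline value could explain variance, but no term for it is assigned.

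Lavage adds to this in synovial fluid. A pair lavaged at one visit only shows a large apparent change with no biology behind it. Fixing the instilled volume at 10 ml does not fix the dilution, which depends on how much fluid was in the joint. Such pairs are also the values most likely to be called outliers, and there the plan has two rules that disagree.

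Aim 1 rests on two small arms: 92/4 = 23 each, or the 30-31 stated in Section 11.2. Power lost here can hide a real biomarker effect.

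**Working it through.** **The plan's own figure.** The 90% power in Section 11.5 reproduces as a three-group F test with effect size read as f² = .2, N = 92 and alpha .01: noncentrality .2 × 92 = 18.4, df 2 and 89, power .901. It says nothing about response scale or baseline adjustment, so it does not bear on this point.

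**Assumed inputs.** The documents give no SD, correlation, effect ratio, dry-tap rate or residual volume. Everything below is illustration: lognormal marker, 31 per arm, two-sided alpha .05, r = correlation of log baseline with log 6-week value. The SD on the log scale is s = √ln(1+CV²), which is .833 at CV 100%.

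**Step 1: scale and baseline, no lavage.** At CV 100%, r = .5 and a 40% reduction, the log effect is −ln(.6) = .511.
- Log ratio, unadjusted: SE = .833 × √(2(1−.5)) × √(2/31) = .2116; .511/.2116 = 2.42; power about 66%.
- Log-ANCOVA: SE = .833 × √(1−.25) × √(2/31) = .1832; .511/.1832 = 2.79; power about 78%.

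Fractional change has no such simple formula. Simulated power (8,000 runs per cell, error about 1 point):

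| Setting | r | Fractional, unadjusted | Fractional + log baseline | Wilcoxon on fractional | Log-ANCOVA |
|---|---|---|---|---|---|
| CV 100%, 40% reduction | .3 | 37% | 47% | 49% | 69% |
| | .5 | 53% | 62% | 63% | 78% |
| | .7 | 79% | 84% | 84% | 91% |
| | .85 | 98% | 99% | 99% | 99% |
| CV 50%, 30% reduction | .3 | 63% | 78% | 67% | 86% |
| | .5 | 79% | 87% | 81% | 91% |

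In the r = .5, CV 100% cell the loss is .776 − .532 = 24 points, about half from scale (53 to 66%) and half from baseline adjustment (66 to 78%). Over all 32 cells (23 or 31 per arm) log-ANCOVA gains 0 to 32 points over unadjusted fractional change. At alpha .01 the same cell gives 25% against 54%. With no true effect every method rejects 4-6% of the time.

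**Step 2: size of the dilution.** For residual volume V ml, dilution D = (V+10)/V, so V = 2 gives 6-fold and V = 10 gives 2-fold. With no true change, lavage at baseline only gives a fractional change of D − 1 = +500% at V = 2; lavage at 6 weeks only gives 1/D − 1 = −83%. At an assumed 10% dry taps per visit, 2 × .1 × .9 = 18% of pairs are mixed.

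**Step 3: power with lavage** (CV 100%, r = .5, 40% reduction, 10% dry taps in both arms at both visits, V from 2 to 10 ml):
- fractional change: 21-47% (about 21-22% at V = 2)
- Wilcoxon on fractional change: 43-60%
- log-ANCOVA without lavage terms: 54-74%
- log-ANCOVA with a lavage indicator for each visit: 75-77%
- undiluted pairs only, log-ANCOVA: 67-70%

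**Step 4: false positives with lavage, no true effect.** With equal 10% dry-tap rates, 4-5% for all methods. With 6-week rates of 10% in one arm and 30% in the other: fractional 6-7%, Wilcoxon 8-19%, log-ANCOVA without indicators 10-27%, with indicators 5-6%. If, in addition, drier knees have lower marker levels (assumed correlation .3 to .5, V varying over 2-10 ml): fractional 5-6%, log-ANCOVA without indicators 13%, with indicators 7-9%, undiluted pairs 6-7%.

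**The case against.** Five points on the other side carry weight.

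- **The plan does not forbid any of this.** ANCOVA and confounder adjustment are permitted in general terms, and a GAM can take a link and a smooth for baseline. That stands: the fault is under-specification. A Gamma log-link model of the 6-week/baseline ratio with log baseline gave 63/72/87% against 69/78/91% for log-ANCOVA (CV 100%, 40% reduction, r .3/.5/.7), so it recovers most of the gain.
- **Some assays are already covered.** Delta delta Ct and negative binomial models imply a log scale. The point is therefore confined to concentration-type proteins such as ELISA or multiplex panels.
- **The size is unanchored.** Every SD, correlation and rate is assumed, and the gain is about 1 point or less at r = .85. This stands.
- **Lavage may be recorded or corrected elsewhere.** The CRF appendices and laboratory SOPs are not in the text, so a field or correction cannot be ruled out. The fair statement is that no analysis rule names lavage. The generic confounder rules cannot work unless it is recorded.
- **The study is discovery-based.** True, but Aim 1 has a defined two-arm contrast and its own model.

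A reader might also infer that dilution would create false treatment effects under the planned analysis. The figures do not support that: fractional change holds about 5-7% even when dry taps differ by arm. The 10-27% belongs to a log model that ignores lavage. Nor does the plan limit outlier handling to loose replacement, since Section 11.1 opens with the stricter rule.

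**Conclusion.** The point holds as a cheap improvement. Aim 1's model is fixed as fractional change without a baseline term, family, link or log scale. For skewed protein concentrations that can cost between nothing and 32 points of power, and 24 points in the middle case. Without lavage, type I error is unaffected. In synovial fluid, mixed neat and lavaged pairs can cut power further, from about 53% to about 21% under 10% dry taps and 2 ml residual fluid. Blood measures are untouched by lavage.

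A log scale alone does not cure dilution and, if dry taps differ by arm, makes false positives worse; the two changes belong together. The indicator model is not clean either, because the 6-week indicator is measured after randomisation. Separately, the two outlier rules in Section 11.1 conflict and need reconciling. All sizes rest on the assumptions stated in the working, since the documents supply none of them.

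**What to change.** **Aim 1, concentration-type proteins.** In Section 11.6, model log(6-week value) on arm with log(baseline) as a covariate or smooth term, or use an equivalent log-link GAM with baseline. Report the ratio of geometric means (1 − ratio gives the percent reduction). State a rule for values below detection before logs are taken.

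**Synovial fluid.** Record lavage yes/no at every aspiration. Do not run the log model without handling lavage: include both visit indicators, and present the undiluted-pair analysis beside it, because the 6-week indicator is post-randomisation. Report dry-tap counts by arm and visit.

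**Outliers.** Let the primary analysis follow the opening rule of Section 11.1: remove only verified errors, decided blind to arm. Keep exclusion or replacement of valid values as sensitivity analysis.

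**Cost.** SAP wording, a few lines of R and, if the CRFs lack it, one field per aspiration. The estimand becomes a ratio. The indicators assume similar dilution across lavaged samples; with residual volume varying over 2-10 ml and 10% dry taps they still gave 76% power against 68% without. Lavage status left unrecorded at collection may not be recoverable later.

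### The trial is sized at .01 to allow for false discovery in the primary biomarker set, but section 11.6 tests at 0.05 and adjusts only secondary p-values, so the primary biomarker tests have no stated correction

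*Combined protocol and SAP*

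**What the plan says.** Section 11.5, on sample size: "Significance threshold for power calculations was considered to be .01 to account for false discovery rate within our set of primary biomarker outcomes". The same section claims 90% power with at least 92 participants after attrition and an effect size of .2.

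Section 11.6, on analysis: "Hypothesis tests will be two-tailed and statistical significance will be considered at the putative threshold", given there as 0.05. The next sentence reads "Any secondary P-values will be subject to a false discovery rate adjustment in keeping with best statistical practices".

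On what is primary, 11.6 says "Aim 1 will include biomarker measures only; Secondary Aim 2 will include both biomarker measures and self-reports", and for the first of these, "Aim 1 will be evaluated by comparing the PRP only and the PRP + PBMT treatment arms at six weeks relative to baseline". The IRB approval memorandum at the front of the document gives the primary objective as comparing all four arms on the biology of knee osteoarthritis. Section 11.5 supports its primary comparison with an effect size from a study of control against PBMT.

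Two other places touch on the subject. Section 11.1 lists, among post hoc options, "pairwise univariate tests with false discovery rate correction, depending on the objectives of the analysis". The proteomics paragraph of 11.6 names test statistics and says that this "analysis will be utilized to analyze the primary and secondary outcomes", without a multiplicity rule.

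**The concern.** Section 11.5 acknowledges that the primary outcome is a set of biomarkers and that testing a set calls for an allowance. That allowance is used only to choose the sample size. The section that decides what counts as a finding has a general 0.05 threshold and reserves the adjustment for secondary p-values. The usual order of protection is therefore reversed: the tests that carry the trial's main conclusion have less control than the supporting ones.

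An analyst who followed 11.6 to the letter could report any primary biomarker with p below 0.05 as significant, however many were tested. The harm is to the false-positive rate. Power is not harmed, because testing at 0.05 after sizing at .01 can only raise it.

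**Working it through.** **1. Does the sizing really use .01?** The documents name neither the effect-size metric nor the test. One reading that reproduces the stated figure takes .2 as f-squared in a linear model with 2 numerator degrees of freedom (three groups):

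- noncentrality = f-squared × N = 0.2 × 92 = 18.4, with 2 and 89 degrees of freedom;
- power at .01 = 0.901 (at N = 91 it is 0.897, so 92 is the smallest N that reaches 90%);
- power at 0.05 = 0.973, and 67 participants would give 90%.

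On this reading the stated 90% belongs to .01, so the sizing and analysis thresholds differ. The reading is an assumption. It fits three groups, whereas the trial has four arms; with 3 degrees of freedom the power at .01 is 0.854.

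**2. Is the correction supplied elsewhere?**

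- Section 11.1: the false discovery rate wording is one option among post hoc tests, at the analyst's choice. A two-arm contrast such as Aim 1 has no post hoc step, and the wording does not address multiplicity across biomarkers.
- Section 11.6, DNA/RNA and proteomic paragraphs: methods and software, no error-rate rule.
- Section 11.6, correlation and predictive paragraphs: none.

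**3. Which tests are primary?**

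- Section 11.6 labels the four-arm comparison as Secondary Aim 2, which implies that Aim 1 is primary.
- The IRB memorandum makes the four-arm comparison primary.
- Section 11.5 borrows its effect size from control against PBMT, which is not the Aim 1 contrast.

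Whichever family is classed as primary, 11.6 gives it no correction.

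**4. How large could the effect be?** The number of tests m and their common correlation r are not in the documents, so both are assumed. Section 10.1 names 12 markers that may be assayed but does not call them primary; m = 12 is used only as an upper illustration. For independent tests with all nulls true, the chance of at least one false positive is 1 − (1 − α)^m; for example, 1 − 0.95^5 = 0.226. For correlated tests, the two-sided normal statistics share one common factor, which is integrated out numerically.

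| m | α per test | r = 0 | r = .5 | r = .8 |
|---|---|---|---|---|
| 2 | 0.05 | 0.098 | 0.091 | 0.078 |
| 5 | 0.05 | 0.226 | 0.183 | 0.127 |
| 12 | 0.05 | 0.460 | 0.319 | 0.186 |
| 5 | .01 | 0.049 | 0.042 | 0.030 |
| 6 | .01 | 0.059 | 0.049 | 0.033 |
| 12 | .01 | 0.114 | 0.083 | 0.048 |

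**5. What does .01 correspond to?** The strictest Benjamini-Hochberg step at q = 0.05 is 0.05/m: .01 for m = 5 and .0042 for m = 12. As a flat per-test level, .01 keeps the family-wise rate within 5% for up to 5 independent tests (6 give 5.9%). Positive correlation extends this to 6 tests at r = .5 and 13 at r = .8.

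**The case against.** **This is declared discovery research, with orthogonal validation foreseen.** That limits the harm of a false lead. However, the plan specifies hypothesis tests, a significance threshold and a false discovery rate rule, and a discovery purpose does not explain adjusting secondary but not primary p-values. The sections on validation do not say which threshold selects a marker.

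**Section 11.5 shows that an allowance was intended.** This is fair. The likeliest explanation is that the allowance was not carried from one section to the next. A reader might infer a deliberate choice to leave the primary set uncorrected; the documents do not support that. The wording still needs repair, because 11.6 is the section that will be followed.

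**Aim 1 is not clearly the primary family.** This stands. A reader might infer that the gap is specifically in the Aim 1 tests and that correcting those would close it. That rests on one label in 11.6, which the IRB memorandum contradicts.

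**The size depends on assumptions.** This also stands. The figures are family-wise rates with every null true, whereas the plan's criterion is the false discovery rate. The two coincide only in that all-null case, and the false discovery rate when some markers respond has not been estimated.

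**Conclusion.** The point holds for the primary biomarker tests, however that family is finally defined. Sections 11.5 and 11.6 disagree, and as written the primary set has no multiplicity correction while the secondary p-values do. This conclusion needs no assumption.

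The size does. With all nulls true and correlation from .8 down to zero, the chance of at least one false positive at 0.05 is 8% to 10% for 2 tests, 13% to 23% for 5 and 19% to 46% for 12. It would be wrong to read 46% as the trial's error rate: it requires 12 independent primary tests, and the documents establish neither the number nor the independence.

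The plan should be corrected before analysis. This is not a reason to doubt the trial's power, and the identity of the primary comparison remains to be settled by the sponsor.

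**What to change.** In section 11.6:

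1. State which comparison and which biomarkers form the primary family, and reconcile this with the primary objective in the IRB memorandum and the primary comparison in 11.5. If an appendix already lists the primary biomarkers, cite it.
2. Extend the adjustment to that family, for example: *P-values across the primary biomarker set will be adjusted by Benjamini-Hochberg at q = 0.05.* Leave the secondary adjustment as planned.

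An acceptable alternative to step 2 is to carry the .01 per-test threshold from 11.5 into 11.6 for the primary set, noting that it holds 5% family-wise only up to 5 tests if they are independent. Under either choice, 11.5 should say how .01 relates to the rule adopted.

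The cost is agreement on the primary family before analysis, one sentence of text and a standard adjustment in R. Fewer primary markers will be nominally significant. With Benjamini-Hochberg, power at the strictest step falls below that at .01 once the set exceeds 5 tests: under the reading that reproduces 90% (N = 92, f-squared 0.2, 2 degrees of freedom), from 0.90 at .01 to 0.84 at .0042 for 12 tests. That is a worst case, because later steps are less strict. Carrying .01 across costs no power against the stated calculation.
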